9.0 Research with Vulnerable Populations

NA

10.0 Incomplete Disclosure or Deception:

NA

11.0 Consent Process:

Screening: Interested individuals will complete an online consent form prior to beginning the online screening survey or the shortened screening survey. The online consent form will describe the online screening survey in REDCap.

Eligible individuals who are invited to participate in the eligibility assessment will be asked to complete an online consent form via REDCap prior to beginning the assessment. A PDF copy of the consent form will be emailed to participants prior to the assessment so they can review the form in advance. Then during the assessment, an approved member of the research team will explain the study and procedures, and participants will be allowed as long as needed to review the consent form and ask any questions they may have. The assessor will then provide the participant with the REDCap link so the participant can e-sign the form. Individuals who do not consent to study procedures will be unable to participate.

12.0 Waiver of Participant Signature on Consent Form:

N/A

13.0 Waivers and Alterations of Consent Information:

NA

14.0 Financial Compensation:

Compensation will be prorated in the study. Participants will receive increasing amounts for each assessment they complete: \$20 for baseline (eligibility), \$25 for mid-intervention (8-weeks), and \$30 for post-intervention (16-weeks). To encourage participants to complete all assessments, they can earn an additional \$15 for completing all assessments. This means participants have potential to be compensated \$90 total for completing all study activities. Hyperwallet electronic gift cards (e-gift cards) will be provided to participants. Hyperwallet e-gift cards may be used anywhere Visa is accepted. Participants also will be allowed to keep their electronic scale. Participants will not be compensated for completing the intervention or communicating with their coach.

1.0 Audio/Video Recording/Photography

Interview assessments will be audio and/or video recorded to assess reliability of assessors in administration or for subsequent qualitative analyses.

After each session, audio and/or video files will be transcribed (e.g., automatically by Zoom, manually by an approved research member) and the recordings and transcriptions will be uploaded to the FSM research files and removed from the recording device. Additional edits may be made to the transcription files by an approved research team member. All transcripts of the recordings will be de-identified. Recordings and transcripts will be stored on password protected computers and secure servers only accessible to approved study staff.

15.0 Potential Benefits to Participants:

Participants may experience reductions in weight and binge eating, as well as improvements in core psychopathology (i.e., overvaluation of weight and shape, unhealthy weight control practices, and negative affect). These changes have potential to reduce the onset or maintenance of medical problems and total health care service use and costs associated with obesity and binge eating. Participants may also benefit from knowing that their use of the intervention and feedback will help inform improvements to the intervention that may improve the precision and efficacy of care for individuals with obesity and binge eating. All participants will be provided with referral information for treatment following the trial.

16.0 Risks to Participants:

There are minimal risks associated with participating in the study. Potential risks that might exist fall into the following four categories: (a) risks associated with the intervention; (b) risks associated with study assessments; (c) risks associated with potential loss of confidentiality; and (d) risks of worsening symptoms.

- (a) Risks associated with the intervention: Digital mental and behavioral health interventions have not been shown to cause any harm. All intervention activities are optional, and participants can discontinue using the intervention at any time, while still participating in the study.
- (b) Risks associated with study assessments: Study assessments include questions about eating disorder behaviors and other mental and emotional problems that may make study participants experience discomfort or anxiety. All participant responses to assessment questions are voluntary; they are told that they can decline to answer any questions that they choose or stop the assessment. The instruments and methodologies used throughout the study are well tested and are not known to cause problems or distress on the behalf of the participants.

- (c) Risks associated with potential loss of confidentiality. Every possible measure will be taken to minimize the potential risk of loss of confidentiality. For use of the intervention, transmissions are protected using a Transport Security Layer and communication occurs within a secure messaging platform; however, there is the possibility that others may see the participant's open webpage or smartphone. There is also the possibility that databases may be hacked. There is the potential risk of breach of confidentiality or loss of identifying information due to the use of Zoom (a 3rd party vendor contracted with Northwestern that requires NU credentials to use but is not HIPAA-compliant) and internet-based phone services (e.g., Zoom, Google Hangouts/Voice, CiscoJabber). A research team member will explain all risks involved with the study during the consent process and answer any questions the participant has about this. There is also the remote possibility that research records will be subpoenaed by a court of law. All these potential losses of confidentiality will be disclosed in the consent documents.
- (d) Risks of worsening symptoms: There is potential for participants to show no change or worsening in binge eating or weight. It is not believed that the risk of these or other adverse outcomes are increased as a function of being enrolled in this study. If a participant does not show symptom improvement following the intervention or at the follow-up assessment, this individual will be offered treatment referral information. Individuals also may request this information at any point during the active intervention period. If any participant appears to be in crisis during the intervention or assessments, appropriate action will be taken based on an established crisis assessment protocol.

17.0 Provisions to Protect the Privacy and Confidentiality of Participants and the Research Data:

The overall risks for study participation are minimal, and any possible risk will be minimized as much as possible. Personal identifiers, namely via video/audio recordings, will be obtained. Identifying information will be obtained with the screen to allow for the study team to contact the potential participants to schedule the eligibility assessment. Participants' identifying information will be kept private. All participants will receive a study ID to protect their identity during assessments and for data analysis.

All self-report questionnaire data collection will occur using a REDCap survey. REDCap is a secure, web-based data collection and management software program that will be accessible to only approved study members. Research interviews will occur by video or telephone call, and questionnaires will be e-mailed as a link for participants to complete on their own. For these sessions, participants will be encouraged prior to and on the day of to find a private space

to complete the call and questionnaires, and not while driving. Participants using the intervention will create a unique password to use with the intervention. Passwords will only be known to participants.

Participant data that are exported from the mobile intervention will be uploaded to the secure, password-protected FSM research servers. Following the study, all intervention use data will be removed from the intervention host platform. All study-related records (e.g., consent forms, payment materials, study assessment data) will be stored for at least 3 years following the end of the study in locked file cabinets, on secure, password-protected servers, and/or password-protected file or software program(s) (e.g., REDCap, StudyTracker). Only approved study staff will have access to a password-protected file or software program(s) (e.g., REDCap) that link participants with their study IDs and usernames. Among individuals who complete the verbal consent, data collected from the online screeners will be retained for research purposes in the event that information needs to be reported (e.g., for research publications) comparing differences between eligible and non-eligible participants. Audio and/or video recordings will be kept on secure, password-protected files (i.e., FSM research files) and removed from the audio recording device after they are uploaded.

18.0 Data Monitoring Plan to Ensure the Safety of Participants:

Any participants who do not show symptom improvement by the end of the intervention will be offered referral information for treatment. The principal investigator will be responsible for assembling the data safety and monitoring data and producing data safety and monitoring reports. Information will be documented on each participant who drops out of the study. Results of participant accrual and retention will be presented to the study team on a monthly basis.

There is the potential for lack of improvement or worsening of symptoms. To ensure participant safety, the principal investigator will keep a log of any issues perceived to be related to testing or the intervention or that might require further assessment or attention. Any potentially adverse events will be evaluated by the principal investigator within 72 hours. Serious adverse events will be promptly reported to the IRB at Northwestern University and to the NIH; all other adverse events will be included in the annual report to the NIH.

19.0 Long-term Data and Specimen Storage and Sharing:

Data generated from this project may be shared with other investigators who provide a proposal with a strong research question and appropriate rationale and analytic plan. In such a case, data would be de-identified as per HIPAA regulations to protect the confidentiality of participants, and the investigators would work closely together to ensure high quality output and meet all compliance regulations of participating institutions.

20.0 Qualifications of Research Team to Conduct the Research:

The study team has expertise spanning all areas required to successfully conduct this study. **[name]**'s research program focuses on designing, optimizing, and implementing digital interventions, primarily for eating disorders and obesity. She has been working on trials of digital interventions for more than 12 years. **[name]** is a renowned leader in the treatment of eating disorders and obesity, specializing in evaluating mechanisms of aberrant eating pathology.

References

1. Steirman B, National Center for Health S. *National Health and Nutrition Examination Survey 2017 - March 2020 prepandemic data files : development of files and prevalence estimates for selected health outcomes*. National health statistics reports no 158. U.S. Department of Health and Human Services, Centers for Disease Control and Prevention, National Center for Health Statistics; 2021.

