Two in five U.S. adults have obesity,¹ which is associated with morbidity, mortality, and high healthcare costs.²⁻⁴ Up to 30% of adults with obesity engage in binge eating,⁵ an eating disorder behavior characterized by eating a large amount of food and experiencing a loss of control while eating.⁶ Binge eating causes excess weight gain, undermines weight control treatment outcomes, and confers risk for comorbidities including metabolic syndrome.^{7,8} Despite their substantial overlap and tendency to persist in the absence of treatment, no intervention sufficiently addresses both obesity and binge eating,⁹⁻¹¹ which results in a pressing clinical gap.

To fill these gaps, we created FoodSteps, the first intervention for both obesity and binge eating, delivered by mobile device to increase scalability. In the first trial of FoodSteps (K01 DK116925; PI [name]), we rigorously designed the intervention with user input and tested its feasibility. Preliminary findings show that FoodSteps is engaging with high rates of completion and adherence, unlike most apps.¹² But, FoodSteps has not been adapted for nor tested among a subpopulation of people with binge eating, obesity, and food insecurity.

Food insecurity, defined as inadequate/inconsistent access to food required for a healthy life,¹³ is increasingly being linked to binge eating.¹⁴ Only 9 people (15%) who enrolled in the K01 clinical trial reported having food insecurity, as recruitment was not designed to target this subpopulation. To inform a future R01 clinical trial of FoodSteps among people with food insecurity, we need to pilot test this intervention among a larger sample. Additionally, FoodSteps has not been tested in people with weight-related health problems such as type 2

diabetes mellitus, a clinically important extension given the prevalence (up to 20%) and negative impact of binge eating among people with diabetes.^{15,16}

Therefore, the overarching goal of this study is to conduct a pilot test of the FoodSteps intervention among adults with recurrent binge eating, Type 2 diabetes, and food insecurity to determine its feasibility, acceptability, and preliminary efficacy among this population.

2.0 Enrollment Criteria:

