Coaching: Each participant will be assigned a coach, who is trained and supervised weekly by a clinical psychologist. Coaching follows a low-intensity model aimed at encouraging participants to use the intervention and practice skills in their daily lives, as well as provide some technical support as needed. Coaches will use messaging such as text or e-mail to communicate with participants through a password-protected website on a secure server. Coaching will begin with an initial ~30-minute phone call to establish goals and build rapport, ensure the participant can access the intervention, set expectations for the coach-participant relationship, and make the participant aware that they can request treatment referral information any time as well as explain how to navigate to the intervention's Resources page which includes treatment referral information. Thereafter, participants will receive ~1-2 messages per week from their coach to offer encouragement, reinforce app use, and check-in on progress or challenges. Coaches also will aim to respond to participant-initiated messages within 1 working business day. An optional ~10-minute call at week 8 (mid-way through the intervention) will be offered to participants to check in on their progress, with potential for additional calls as needed. After participants schedule their coaching call, they may receive emails and/or text messages (up to 4) reminding them of their upcoming appointment. Participants who have already consented into the study will not receive text message reminders.

Study assessments will occur again at mid-intervention (8-weeks) and post-intervention (16-weeks). Baseline (i.e., the eligibility assessment), mid-intervention, and post-intervention assessments will include interviews and/or questionnaires. After participants schedule their research assessments, they may receive emails and/or text messages (up to 4) reminding them of their upcoming appointment. Participants who have already consented into the study will not receive text message reminders. Interviews and questionnaires will assess the following topics: personal and demographic information, treatment and stipend utilization, height, weight, number of binge episodes over the past three months, eating-related symptoms, stress, shame, food security, and experiences with technology. The following questionnaires will be administered via a

REDCap survey link:

Measure	Timepoint		
	Baseline	Mid-intervention	Post-intervention

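### Adverse events, including diabetes-related ones, are not a listed topic at week 8 or 16 and reach the record only through an investigator-judged log, so their frequency cannot be estimated

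*Protocol*

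**What the plan says.** Section 18.0 is the only place that says how adverse events are recorded: "the principal investigator will keep a log of any issues perceived to be related to testing or the intervention or that might require further assessment" (the sentence ends by adding attention to assessment). Two further sentences follow. One says "Any potentially adverse events will be evaluated by the principal investigator within 72 hours". The other has serious events reported promptly, while "all other adverse events will be included in the annual report to the NIH".

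Section 8.0 fixes when participants are seen: "Study assessments will occur again at mid-intervention (8-weeks) and post-intervention (16-weeks"). After personal details and use of treatment and of the stipend, it lists the topics as "height, weight, number of binge episodes over the past three months, eating-related symptoms, stress, shame, food security, and experiences with technology". The questionnaire table in the same section has, at both times, the Eating Questionnaire, CIA 3.0, CESDR-10, the food insecurity screener, the System Usability Scale, Treatment Utilization, the Perceived Stress Scale and the Personal Feelings Questionnaire. At week 16 it adds a stipend and an implementation questionnaire. Neither list has an entry for adverse events or for diabetes-related events.

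On the population, the background states: "Additionally, FoodSteps has not been tested in people with weight-related health problems such as type 2" diabetes. Section 16.0 bases the risk of the intervention on digital interventions in general: "Digital mental and behavioral health interventions have not been shown to cause any harm". None of its four risk categories mentions diabetes.

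**The concern.** An event has to pass two steps before it is on record. It must come to light, and the protocol does not say that anyone asks. The investigator must then see it as related, or as possibly needing follow-up. An event that fails either step leaves no trace in the only record described.

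Two things are at stake. First, the number of logged events depends on how events happened to be noticed and judged as well as on how many occurred, so it cannot be read as a frequency. This matters most for diabetes-related events, because the protocol itself calls this population untested. Second, Section 18.0 promises that all non-serious adverse events go into the annual report. A log with entry conditions and no stated elicitation cannot reliably supply that report.

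This is a protocol matter. A later analysis plan cannot recover events that nobody asked about or wrote down.

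**Working it through.** The protocol states no event rate and gives no calculation for its sample size, so there is no figure to reproduce. The check is mainly a comparison of text.

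**1. What is collected from everyone, and what is not**

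| Kind of information | Where | Collected systematically? |
|---|---|---|
| Worsening of binge eating or weight (harm named in Section 16.0(d)) | Section 8.0, weeks 8 and 16; scale weights also automatic | Yes |
| Depressive symptoms, stress, impairment | CESDR-10, Perceived Stress Scale and CIA 3.0 in the Section 8.0 table | Yes |
| Use of other treatment | Treatment Utilization in the Section 8.0 table | Yes, but not described as event capture or linked to Section 18.0 |
| Dropout | Section 18.0 | Yes, information documented for each case |
| Any other new or worsened health problem | Section 18.0 log only | No item listed |
| Diabetes-related events, or diabetes medication changes after entry | Section 18.0 log only | No item listed |

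Section 2.0 allows exclusion of people whose diabetes medication was recently started or changed. The protocol thus treats such changes as relevant at entry but lists no matching item afterwards.

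**2. The entry rule against the reporting rule**

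- Entry to the log: perceived relation to testing or the intervention, or possible need for follow-up.
- Evaluation within 72 hours: any potential adverse event, with no condition on relatedness.
- Annual report: all non-serious adverse events, with no condition on relatedness.

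The last two rules are wider than the first. A non-serious event judged unrelated and of no concern belongs in the annual report but need not enter the log. An event that is never mentioned enters neither.

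**3. Illustration: what a zero count would mean**

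Inputs: n = 40, the maximum in Section 3.0, assuming full enrolment and an answer from everyone. With 0 events, the one-sided 95% upper bound on the proportion with an event is

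1 − 0.05^(1/40) = 0.072, or 7.2%.

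The two-sided 95% Clopper-Pearson upper limit is 8.8%. If only a share s of affected participants reaches the log, the one-sided bound on the true proportion becomes 7.2%/s. The protocol gives no basis for s, so an empty log yields no usable bound.

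**4. Illustration: what the fix could show**

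With everyone asked, and event rates that are assumptions:

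- rate 5%: expected number 40 × 0.05 = 2; chance of seeing at least one 1 − 0.95^40 = 0.871
- rate 10%: expected number 40 × 0.10 = 4; chance of seeing at least one 1 − 0.90^40 = 0.985

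A pilot of this size can therefore describe frequent events and little else.

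**The case against.** The strongest reply is that the protocol does watch for harm. The harm it names, worsening of binge eating or weight, is measured in every participant at weeks 8 and 16. So are mood, stress, impairment and treatment use, and dropouts are documented. Coaches under weekly supervision send about one or two messages a week, ask how participants are getting on and offer a call at week 8. There is a crisis procedure. Use of the intervention is optional, and safety is not among the aims.

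Much of this stands, and it rules out several stronger readings:

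- A reader might infer that the pilot cannot show how well FoodSteps is tolerated. The systematic measures above bear directly on tolerability, which is in any case not a stated aim, so no aim fails.
- A reader might infer that only related events are logged. The rule has a second route, for issues that may need follow-up, and the evaluation and reporting sentences carry no condition on relatedness.
- A reader might infer that a near-empty log would go into the R01 as proof of low risk. Aim 3 carries forward efficacy estimates to power that trial; nothing says the log is used this way.
- A reader might put a number on the undercount. An assumed capture share of one half would turn 7.2% into 14.4%, but no share has support in the protocol, so this does not measure the gap.
- A reader might treat the general no-harm sentence in Section 16.0 as an error in itself. The background openly says FoodSteps is untested in type 2 diabetes, so the limit is disclosed.

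The interview guides and the content of Treatment Utilization are not shown. It can be said only that no event item is listed, not that none will be asked.

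What the reply does not answer is the remaining gap. Coaching contacts are not linked to the log, both routes into the log depend on judgement, and health problems outside the listed measures have no stated elicitation.

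**Conclusion.** The point holds in a limited form. Adverse events other than those covered by the systematic measures, including diabetes-related ones, are recorded only if they come to light and the investigator judges them related or possibly in need of follow-up. Their frequency cannot be estimated from this pilot, and the commitment to report all non-serious adverse events cannot be reliably met.

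The size of the undercount is unknown. The 7.2% bound for 0 of 40 only shows what complete questioning could support; it assumes that all 40 enrol and answer and that asking captures every event. The conclusion rests on the listed topics and questionnaires being complete. If the interview guide already has an event question, the protocol need only say so and connect it to Section 18.0.

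No stated aim fails, but the gap is cheap to close now and cannot be repaired after data collection.

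**What to change.** - **Section 18.0:** log every untoward event regardless of perceived relation, with relatedness as a separate field.
- **Section 8.0:** at the existing week 8 and week 16 assessments, ask every participant one open question on new or worsened health problems and one on diabetes-related events or changes in diabetes medication. Add both to the topic list and send the answers to the log.

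The cost is two questions at assessments already scheduled and a short amendment, with no added visits. The downside is more unrelated events to log and a less favourable-looking safety table. With a single arm of at most 40, the result will describe only frequent events and cannot attribute any of them to FoodSteps; the report should say so.
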